10.2.3. Expired CO Levels

Expired CO levels (ppm) will be measured every week from Week 2 to Week 12, then at Week 16, Week 20, and Week 24.

Summary tables and figures of expired CO levels by treatment arm and visit will be provided for the All Randomized Set.

The treatment arms will be compared (cytisinicline 6 weeks vs placebo, cytisinicline 12 weeks vs placebo) using repeated-measures analysis of variance models with fixed effect term for treatment arm, visit and visit * treatment arm interaction. A compound symmetry covariance matrix will be used. The between-arm difference in means, their respective 95% CIs and Bonferroni-adjusted p-values will be reported. Forest plots may be used to display 95% CIs for the differences of the means.

An additional analyses will be performed by abstinence status for the primary endpoint (Weeks 3 – 6 and Weeks 9 -12).

10.2.4. Use of Non-cigarette Nicotine Products

At each study visit from Week 2 through Week 24, subjects will be asked whether they have used (yes, no) any non-cigarette nicotine products since the previous clinic visit. The name of any product used during the interval will be recorded in the CRF (eg, pipe tobacco, smokeless tobacco, e-cigarettes/vaping).

The number (%) of subjects reporting use of non-cigarette nicotine product will be summarized by treatment arm and visit for the All Randomized Set. The summary table will report both the number (%) of subjects using any non-cigarette nicotine product and the number (%) of subjects using each specific product. The summary table will include visits from Week 2 to Week 24, as well as the following study periods: Week 2 to Week 24 (Entire Study Period), Week 2 to

Week 12 (Treatment Period), and Week 16 to Week 24 (Follow-up Period). For the summary by study periods, multiple occurrences of the same nicotine product within a subject will be counted only once.

Statistical comparisons between treatment arms (Arm B vs Arm A; Arm C vs Arm A) will be performed for the Treatment Period and the Follow-up Period. For each period, Fisher's Exact Tests will be used to compare treatment arms in terms of the incidence of using any non-cigarette nicotine products.

10.2.5. Abstinence from Week 9 to Week 12: Arm B vs. Arm A

The statistical methods for this binary endpoint will follow the specifications as described for the secondary objectives.

10.2.6. Continuous Abstinence from Week 3 to Week 24 (Subset Analysis)

The summaries and statistical analyses of the continuous abstinence from Week 3 to Week 24 binary endpoint will include the subset of subjects who achieve abstinence from Week 3 to Week 6 (ie, subset of subjects who are a success on the primary efficacy endpoint for primary objective 1) and have continuous abstinence to Week 24. The statistical methods for binary endpoints will follow the specifications as described for the secondary objectives.

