3.3. Other Objectives

1. To compare arms (Arm B vs Arm A, Arm C vs Arm A) on 7-day point prevalence abstinence weekly at Week 2 through Week 12, then at Weeks 16, 20, and 24.
2. To compare arms (Arm B vs Arm A; Arm C vs Arm A) on serum cotinine levels every other week at Week 2 through Week 12, then at Weeks 16, 20, and 24.
3. To compare arms (Arm B vs Arm A; Arm C vs Arm A) on expired CO levels every week at Week 2 through Week 12, then at Weeks 16, 20, and 24.
4. To compare arms (Arm B vs Arm A; Arm C vs Arm A) on use of any non-cigarette nicotine products, including vaping, during study treatment (Week 2 through Week 12) and study follow-up (Week 16 through Week 24).
5. Assess whether subjects randomized to Arm B have a higher probability of abstinence from Week 9 to Week 12 as compared to subjects randomized to Arm A (placebo).
6. Assess among the subset of subjects who achieve abstinence from Week 3 to Week 6, whether subjects randomized to Arm B have a higher probability of continuous abstinence from Week 3 to Week 24 post-randomization as compared to homologous subjects randomized to Arm A.
7. Assess among the subset of subjects who achieve abstinence from Week 3 to Week 6, whether subjects randomized to Arm C have a higher probability of continuous abstinence at Week 24 post-randomization as compared to subjects randomized to Arm B.
8. Assess among the subset of subjects who achieve abstinence from Week 9 to Week 12, whether subjects randomized to Arm C have a higher probability of continuous abstinence from Week 9 to Week 24 post-randomization as compared to homologous subjects randomized to Arm A.
9. Among subjects who achieve abstinence from Week 3 to Week 6, compare time to failure to maintain abstinence between arms (Arm B vs Arm A, Arm C vs Arm A) to Week 24.
10. To explore the magnitude of treatment effect between arms across various subgroups defined by demographic and baseline characteristics for the primary and secondary outcomes.
11. To explore potential relationships between subject-reported outcomes (eg, anxiety, depression, tobacco craving) and the primary and secondary outcomes.

12. To assess possible withdrawal symptoms at Week 7 in Arm B subjects who will have discontinued cytisinicline at Week 6, analyzing separately for nicotine status (eg, either smoking, abstinent, or if using other nicotine products including vaping or nicotine replacement therapy [NRT]) compared to Arms A and C.

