4.1.3. Other Efficacy Endpoints

In general, the other efficacy endpoints defined in this section are associated with tertiary efficacy objectives. The other efficacy endpoints are:

7-day point prevalence abstinence is a binary endpoint (success, failure) at each visit from Week 2 through Week 24. At each visit, success will be defined for a subject as having reported smoking abstinence with biochemical verification (CO<10 ppm). 7-day point prevalence for smoking abstinence will be defined as reporting no smoking since the last clinic visit at each weekly clinic visit from Week 2 through Week 12 and over the past 7 days during Follow-up visits at Weeks 16, 20 and 24. Any other outcome will be regarded as a failure. All subjects will have a realization of this endpoint, thereby enabling analyses that follow the ITT principle without imputation.

Serum cotinine levels (ng/mL) are a continuous endpoint measured every other week from Week 2 to Week 12, then at Week 16, Week 20, and Week 24.

Expired CO levels (ppm) are a continuous endpoint measured at each visit from Week 2 through Week 24.

Use of non-cigarette nicotine products, including vaping, will be assessed at each visit from Week 2 to Week 24. Subjects report whether they have used any non-cigarette nicotine products since the last visit (yes, no) and report all products used during the interval (eg, pipe tobacco, e-cigarettes/vaping, marijuana smoking/vaping).

Continuous abstinence from Week 3 to Week 24 (subset analysis): Assess among the subset of subjects who achieve abstinence from Week 3 to Week 6 in Arm A and Arm B (ie, are a

success on the primary efficacy endpoint for primary objective 1). Success will be defined for a subject following the same rules as the continuous abstinence endpoint (see Section 4.1.2.1).

Continuous abstinence from Week 9 to Week 24 (subset analysis): Assess among the subset of subjects who achieve abstinence from Week 9 to Week 12 in Arm A and Arm C (ie, are a success on the primary efficacy endpoint for primary objective 2). Success will be defined for a subject following the same rules as the continuous abstinence endpoint (see Section 4.1.2.1).

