10.2.7. Continuous Abstinence from Week 9 to Week 24 (Subset Analysis)

The summaries and statistical analyses of the continuous abstinence from Week 9 to Week 24 binary endpoint will include the subset of subjects who achieve abstinence from Week 9 to Week 12 (ie, subset of subjects who are a success on the primary efficacy endpoint for primary objective 2) and have continuous abstinence to Week 24. The statistical methods for binary endpoints will follow the specifications as described for the secondary objectives.

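### SAP 10.2.6 and 10.2.7 make continuous abstinence to Week 24 an inclusion criterion for analyses in which it is the outcome, and do not say that the drug-versus-placebo contrasts in these subsets are not randomized comparisons

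*SAP*

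**What the plan says.** The analysis instruction in SAP 10.2.6 is for a binary endpoint, continuous abstinence from Week 3 to Week 24. It restricts the analysis to the "ie, subset of subjects who are a success on the primary efficacy endpoint for primary objective 1) and have continuous abstinence to Week 24". SAP 10.2.7 has the matching restriction for Weeks 9-12: "ie, subset of subjects who are a success on the primary efficacy endpoint for primary objective 2) and have continuous abstinence to Week 24". Both sections send the reader to the methods for the secondary objectives. SAP 10.1.3 in turn sends the reader to the primary method in SAP 10.1.2, the exact odds ratio test stratified by site.

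The endpoint definition in SAP 4.1.3 is different. For the first of these endpoints it reads "Assess among the subset of subjects who achieve abstinence from Week 3 to Week 6 in Arm A and Arm B", and the outcome is a separate step: "Success will be defined for a subject following the same rules as the continuous abstinence endpoint". The objectives in SAP 3.3, repeated in Protocol 6.3, agree with 4.1.3. Objective 6 begins "Assess among the subset of subjects who achieve abstinence from Week 3 to Week 6, whether subjects randomized to Arm B" and objective 8 begins "Assess among the subset of subjects who achieve abstinence from Week 9 to Week 12, whether subjects randomized to Arm C". Each then asks whether the drug arm has the higher probability of continuous abstinence to Week 24, compared with what the objectives call homologous placebo subjects.

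SAP 10.2 points to 4.1.3 for the definitions of these endpoints and labels the analyses exploratory, without multiplicity protection. The Week 24 comparisons in all randomized subjects are the secondary endpoints (SAP 4.1.2.1 and 10.1.3).

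**The concern.** There are two separate problems.

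The first is that the rule deciding who is analysed already contains the result to be analysed. A programmer who follows 10.2.6 or 10.2.7 as written gets a table without failures.

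The second remains after that is corrected. Abstinence in Weeks 3-6 or 9-12 is the primary efficacy endpoint, and the trial is designed on the expectation that the drug raises it. Those who quit on placebo and those who quit on drug may therefore be different kinds of smoker, and randomization does not make the two groups comparable. The SAP has no caution to this effect, and calling the placebo abstainers homologous suggests the opposite. The exploratory label deals with multiplicity, not with selection. What is at stake is how an odds ratio and P value from these subsets will be read: they could be taken for a drug effect on staying abstinent when part or all of the difference reflects who entered the subset.

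**Working it through.** **1. The texts side by side**

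| Place | Who is analysed | Outcome |
|---|---|---|
| SAP 10.2.6 | Week 3-6 successes who are also continuously abstinent to Week 24 | continuous abstinence to Week 24 |
| SAP 10.2.7 | Week 9-12 successes who are also continuously abstinent to Week 24 | continuous abstinence to Week 24 |
| SAP 4.1.3; objectives 6 and 8 | Week 3-6 (or Week 9-12) successes | continuous abstinence to Week 24 |

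SAP 10.2.8, on time to failure, also takes the Week 3-6 successes alone.

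**2. The literal rule.** With a placebo and b drug subjects included, the table is a successes and 0 failures against b successes and 0 failures. The odds ratio is (b × 0)/(a × 0) = 0/0. With a = 18 and b = 48, Fisher's exact test returns p = 1.0 and no odds ratio; any other counts give the same result.

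**3. The plan's own figure.** The documents give no size or power for these subset analyses. The only sizing figure is 95.7% power for each primary comparison (250 per arm, 7% versus 19%, Fisher's exact test, one-sided 0.0125). Exact enumeration gives 95.75%, so it reproduces.

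**4. Subset size after correction.** Rates of abstinence in the primary window are not given for this trial. Two stand-ins from the documents are the sizing rates, which are Week 24 rates (7% and 19%), and the Phase 2b Week 5-8 rates (8% and 30%, Protocol 4.3).

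- 250 × 0.07 = 17.5 and 250 × 0.19 = 47.5: about 18 placebo and 48 drug subjects.
- 250 × 0.08 = 20 and 250 × 0.30 = 75.

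**5. Selection, first illustration.** All inputs are assumptions. 30% of smokers are quit-prone. Quit rates for quit-prone and other smokers are 20% and 3% on placebo, and 40% and 20% on drug. Quit-prone quitters maintain abstinence at 60% in both arms, and other quitters at rate m in both arms. The drug therefore has no effect on maintenance.

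- Quitters on placebo: 0.3 × 0.20 + 0.7 × 0.03 = 0.081.
- Quitters on drug: 0.3 × 0.40 + 0.7 × 0.20 = 0.26.
- Apparent maintenance on placebo: (0.06 × 0.60 + 0.021 × m)/0.081.
- Apparent maintenance on drug: (0.12 × 0.60 + 0.14 × m)/0.26.

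| m | Placebo | Drug | Gap (points) |
|---|---|---|---|
| 25% | 50.9% | 41.2% | 9.8 |
| 40% | 54.8% | 49.2% | 5.6 |
| 50% | 57.4% | 54.6% | 2.8 |
| 60% | 60.0% | 60.0% | 0 |

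**6. Selection, second illustration.** The assumptions are that everyone who would quit on placebo would also quit on drug and maintains at 60%, that the additional quitters on drug maintain at rate q, and that the drug has no effect on maintenance. For 7% versus 19% and q = 40%, apparent maintenance on drug is (0.07 × 0.60 + 0.12 × 0.40)/0.19 = 0.090/0.19 = 47.4%. The subset odds ratio is (0.474/0.526)/(0.60/0.40) = 0.60. In all randomized subjects the Week 24 rates are 4.2% and 9.0%, an odds ratio of 2.26.

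| q | Subset OR, 7%/19% | All-randomized OR | Subset OR, 8%/30% | All-randomized OR |
|---|---|---|---|---|
| 60% | 1.00 | 2.93 | 1.00 | 4.35 |
| 50% | 0.77 | 2.59 | 0.74 | 3.72 |
| 40% | 0.60 | 2.26 | 0.55 | 3.12 |
| 30% | 0.46 | 1.93 | 0.41 | 2.55 |

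The widest gap here is 60.0% versus 38.0%, or 22 points (8%/30%, q = 30%). In both illustrations the gap disappears when the two kinds of quitter maintain equally. It would reverse if the additional quitters maintained better.

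**7. Arm C versus Arm B.** Both arms are assigned 3 mg three times daily through Week 6 (Protocol 7.2). Selection on Weeks 3-6 therefore works alike in the two arms, and objective 7 does not share the problem. This holds for the Week 3-6 subset only.

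**The case against.** The first problem is a drafting slip. SAP 10.2 names 4.1.3 as the place where these endpoints are defined, 4.1.3 is workable, and 10.2.6 itself calls the endpoint binary, which would be pointless if everyone were a success. A reader might infer that the SAP leaves no usable analysis. The documents do not support that, since the intent can be recovered from 4.1.3 and the objectives. What stands is that the operative instruction is wrong in two sections and conflicts with the definition.

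A reader might also infer that these tests could declare the drug harmful to maintenance. Under SAP 10.1.2, a comparison in which the point estimate does not favour cytisinicline is designated not statistically significant, and 10.2.6 and 10.2.7 inherit that method through 10.1.3. An unfavourable estimate, its interval and a two-sided P value could still be printed, so the concern is about interpretation and not about a formal finding of harm.

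Third, the size rests on invented inputs. That is right. It is plausible that placebo abstainers are the more quit-prone group, but the documents do not establish it, and equal maintenance gives no gap at all.

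Finally, a reader might infer that the Arm B versus A and Arm C versus A tests should be dropped. Protocol objectives 6 and 8 ask for these comparisons, and SAP 13 declares no change from the protocol's analyses. Dropping the tests would depart from both, and a caveat meets the concern.

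**Conclusion.** The point holds on both counts, at low severity. The inclusion rules in SAP 10.2.6 and 10.2.7 are wrong as written and contradict SAP 4.1.3 and objectives 6 and 8; this follows from the text and needs no assumption. After correction, Arm B versus A and Arm C versus A in these subsets condition on a post-randomization outcome affected by treatment, so they are not randomized comparisons and may be biased. Neither the direction nor the size of that bias can be derived from the documents. The 0 to about 10 points against the drug in the first illustration, and the wider range in the second, show only that a misleading contrast is possible. The analyses are exploratory: alpha, sample size and the primary and secondary results are unaffected.

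**What to change.** In SAP 10.2.6 and 10.2.7, delete "and have continuous abstinence to Week 24" from the description of the subset. The analysed set is then the Week 3-6 (or Week 9-12) abstainers, and continuous abstinence to Week 24 is the success/failure outcome, as in 4.1.3.

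Add one sentence to both sections, for example: *Arm B versus A and Arm C versus A in these subsets condition on a post-randomization outcome affected by treatment; they are not randomized comparisons and may be biased, and inference on drug versus placebo at Week 24 rests on the secondary endpoints in all randomized subjects.* Arm C versus B among Week 3-6 abstainers (objective 7) needs no such caveat.

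The cost is a wording change in two SAP sections, to be made before unblinding. It needs no protocol amendment, no additional data and no change to the planned tests.

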10.2.7. Continuous Abstinence from Week 9 to Week 24 (Subset Analysis)

The summaries and statistical analyses of the continuous abstinence from Week 9 to Week 24 binary endpoint will include the subset of subjects who achieve abstinence from Week 9 to Week 12 (ie, subset of subjects who are a success on the primary efficacy endpoint for primary objective 2) and have continuous abstinence to Week 24. The statistical methods for binary endpoints will follow the specifications as described for the secondary objectives.

10.2.8. Time to Failure to Maintain Abstinence

Time to failure to maintain abstinence will be evaluated for the subset of subjects who were classified as a success for abstinence from Week 3 to Week 6. Time to failure (days) will be calculated for individual subjects as described in Section 4.1.3. Subjects who are still abstinent at Week 24 will have time to failure censored at the date of the Week 24 visit.

Time to failure will be summarized by treatment arm; the minimum, maximum, median and 95% confidence interval for the median time to failure reported by the LIFETEST procedure will be reported. A Kaplan-Meier figure of treatment arm by time to failure will be produced.

10.2.9. Relationship Between Treatment Effect and Demographic and Baseline Characteristics

The analyses described below will only be performed for the primary efficacy endpoint (biochemically verified abstinence). The objective of these analyses is to assess the homogeneity of treatment effect within strata (subgroups) defined by potential effect-modifying variables. If both primary comparisons (Arm B vs Arm A, Arm C vs Arm A) performed for the primary efficacy endpoint do not meet statistical criterion (ie, are not statistically significant) then the statistical analyses described below will not be performed. If only one of the comparisons meets

statistical criterion then the analyses described below will be performed using data from only two of the treatment arms.

Strata for continuous effect modifiers will be defined by either logical considerations (eg, age >65 years) or statistical criteria (eg, quantile (median, tertile or quartile) split). The variables (factors) that will be evaluated as effect modifiers include, but are not limited to:

- demographic characteristics (eg, sex, age, race, BMI),
- smoking history variables (eg, duration of smoking, average number of cigarettes the subject reported smoking per day over the past 30 days, number of previous quit attempts, type of cigarettes typically smoked: regular vs menthol, prior smoking cessation treatment with varenicline, bupropion, nicotine patch),
- baseline smoking variables (eg, average number of cigarettes smoked per day over 7 consecutive days as reported in the subject diary, baseline CO (ppm), baseline cotinine (ng/mL)),

For each stratum, the number (%) of subjects within each stratum with biochemically verified abstinence will be reported for each treatment arm. Odds ratios (Arm B vs Arm A, Arm C vs Arm A) and their 95% CIs will also be reported. Forest plots will be used to display the stratum-specific 95% CIs.

10.2.10. Relationship Between Subject-Reported Outcomes and Primary and Secondary Efficacy Endpoints

The correlation of subject-reported outcomes (eg, anxiety, withdrawal symptoms, tobacco craving) with the primary and secondary efficacy endpoints (abstinence, continuous abstinence) will be explored. Descriptive statistics for each of the subject-reported outcome variables will be produced for subgroups defined by success/failure on those endpoints.

10.2.11. Questionnaires

The HADS, QSU-Brief, and MNWS questionnaires will be administered at baseline and after the start of treatment. Scores for each questionnaire will be derived as described in Section 8.6.

Questionnaire scores will be summarized using descriptive statistics. For each score, the actual value, change from baseline and percent change from baseline will be summarized by treatment arm and visit. Only subjects with non-missing results at both the baseline and post-baseline visit will be summarized at each time point.

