The QSU-Brief is a 10-item questionnaire that will be administered Day 0, and at various visits during the treatment period (Day 2, Week 1 through Week 6). Item scores will be assigned using the scoring key pre-printed on the questionnaire (see Appendix 4 of the study protocol). A total QSU-Brief score will be derived for each subject, providing all questions have been answered.

Minnesota Withdrawal Scale (MNWS)

The MNWS is a 9-item questionnaire that will be administered at Day 0, and at various visits during the treatment period (Week 1 through Week 7). Item scores will be assigned using the scoring key pre-printed on the questionnaire (see Appendix 5 of the study protocol). A total MNWS score will be derived for each subject, providing all questions have been answered.

Columbia Suicide Severity Rating Scale (C-SSRS)

The C-SSRS (see Appendix 1 of the study protocol) is an assessment of both suicidal ideation and behavior. Suicidal ideation or risk for suicide (“Yes” to either question 4 or question 5 OR “Yes” to any suicidal behavior question on the C-SSRS) is an exclusion criterion.

The “Screening” version of the C-SSRS assesses suicidal ideation over the past 3 months, and suicidal behavior over the subject’s lifetime. The “Screening” version of the C-SSRS will be administered at SV1. The “Since Last Visit” version of the C-SSRS evaluates both suicidal ideation and behavior since the last assessment. This version of the C-SSRS will be administered at Week 6 and Week 12.

C-SSRS Suicidal Ideation: In both the “Screening” and “Since Last Visit” forms, there are 5 items that assess suicidal ideation. Subjects indicate (Yes/No) whether each of the following applies:

1. Wish to be dead
2. Non-specific active suicidal thoughts
3. Active suicidal ideation with any methods, without intent to act
4. Active suicidal ideation with some intent to act, without specific plan

5. Active suicidal ideation with specific plan and intent.

Each item will be assigned a numeric score (0=No, 1=Yes).

C-SSRS Suicidal Behavior: In both the “Screening” and “Since Last Visit” forms, there are 5 items that assess suicidal behavior. Subjects indicate (Yes/No) whether each of the following applies:

1. Actual attempt (non-fatal)
2. Interrupted attempt
3. Aborted attempt
4. Preparatory acts or behavior
5. Suicidal behavior

Each item will be assigned a numeric score (0=No, 1=Yes).

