10.2. Analyses of Other Efficacy Endpoints

The other efficacy objectives are stated in Section 3.3. The other efficacy endpoints are defined in Section 4.1.3. Analyses of the other efficacy endpoints will be exploratory. There will be no multiplicity protection scheme for these analyses, and the results of these analyses will be labeled as exploratory.

The results for each endpoint will be displayed graphically by treatment arm. Side-by-side bar charts may be used to display categorical endpoints, Kaplan-Meier figures will be used for time-to-event endpoints. For binary endpoints, forest plots may be used to display 95% CIs for the odds ratio.

For each of the other efficacy endpoints identified below, 3 between arm comparisons will be performed, where appropriate:

- Arm B (cytisinicline 6 weeks) vs Arm A (placebo)
- Arm C (cytisinicline 12 weeks) vs Arm A (placebo)
- Arm C (cytisinicline 12 weeks) vs Arm B (cytisinicline 6 weeks) (this comparison will be two-sided)

The statistical analyses that will be performed for binary endpoints will follow the specification as described for the secondary objectives according to whether the comparison is one-or two-sided. For other than binary endpoints, the analysis methodologies are described below.

10.2.1. 7-day Point Prevalence Abstinence

The 7-day point prevalence abstinence endpoints are binary (success, failure) endpoints defined at each of the following visits: Weeks 2 to Week 12, Week 16, Week 20, and Week 24. The analyses of point prevalence abstinence endpoints will be conducted using all subjects in the All Randomized Set. The analysis methodology for binary endpoints was described in secondary objectives.

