- Incidence by SOC and preferred term (PT), in alphabetical order of SOC and PT, for both all TEAE and related TEAE
- Incidence by PT, in decreasing frequency of PT, for both all TEAE and related TEAE
- Incidence of TEAEs that resulted in dose reduction or discontinuation of study drug (ie, action taken with study drug reported as dose reduced, dose interrupted, or drug withdrawn), in decreasing frequency of PT
- Incidence of TEAE by PT and severity (mild, moderate, severe), in alphabetical order of PT

- Incidence of TEAE by PT and relationship (related, not related), in alphabetical order of PT
- Incidence of TEAE by PT for events of special interest: COVID-19

The following summaries will also be produced of TEAEs occurring after Week 6 (occurring after Week 6 or ongoing after Week 6) on the study (see definitions above):

- Incidence by SOC and PT, in alphabetical order of SOC and PT
- Incidence by PT, in decreasing frequency of PT
- Incidence of TEAEs that resulted in dose reduction or discontinuation of study drug (ie, action taken with study drug reported as dose reduced, dose interrupted, or drug withdrawn), in decreasing frequency of PT

The following will also be summarized:

- Incidence of TEAEs that occurred from Week 6 (approximately Study Day 42) visit + 1 day through Week 7 visit (approximately Study Day 49) will be assessed for any possible withdrawal effects when switching to placebo during the first Week 7 timeframe for the cytisinicline 6 weeks arm.
- Incidence of TEAEs by time of onset (Up to Week 6 [approximately Study Day 42] visit and after Week 6 visit through Last Dose)
- Incidence of TEAEs by primary endpoint status

In summaries of AE incidence, if a subject experiences the same AE (preferred term) multiple times that subject will be counted only once for that preferred term. Similarly, if a subject experiences multiple AEs (preferred terms) within the same SOC then that subject will be counted only once for that SOC. When summarizing by severity and relationship, only the AE with the highest severity or relationship will be counted.

A Kaplan-Meier figure of time to first TEAE (ie, time from date of randomization to earliest TEAE start date) will be provided by treatment arm. Subjects with no Adverse events will be censored at their last visit.

In addition to summary tables, the following listings will be produced.

- All AEs

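### No analysis in the SAP delivers Objective 12: MNWS has no Week 6 to Week 7 change, no Arm B contrast with an interval, and no split by nicotine status

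*SAP*

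**What the plan says.** - **The objective.** Objective 12 in SAP 3.3 reads: "To assess possible withdrawal symptoms at Week 7 in Arm B subjects who will have discontinued cytisinicline at Week 6, analyzing separately for nicotine status". It names smoking, abstinent and using other nicotine products as statuses, and Arms A and C as comparators. Protocol 6.3 has the same objective.
- **The data.** MNWS is completed at Day 0 and at Weeks 1 to 7 (SAP 6.4.2; Protocol Table 4). Protocol Appendix 5 leaves its analysis to the SAP.
- **The main MNWS analysis.** SAP 10.2.11: "For each score, the actual value, change from baseline and percent change from baseline will be summarized by treatment arm and visit". It continues: "Only subjects with non-missing results at both the baseline and post-baseline visit will be summarized at each time point".
- **A second use of withdrawal scores.** SAP 10.2.10: "Descriptive statistics for each of the subject-reported outcome variables will be produced for subgroups defined by success/failure on those endpoints".
- **A related safety table.** SAP 11.1 tabulates treatment-emergent adverse events from the day after the Week 6 visit through the Week 7 visit. These "will be assessed for any possible withdrawal effects when switching to placebo during the first Week 7 timeframe for the cytisinicline 6 weeks arm".
- **The general rule on comparisons.** SAP 10.2: "For each of the other efficacy endpoints identified below, 3 between arm comparisons will be performed, where appropriate". The list includes C vs B.
- **Other nicotine use.** SAP 10.2.4: "The number (%) of subjects reporting use of non-cigarette nicotine product will be summarized by treatment arm and visit for the All Randomized Set".
- **Changes from the protocol.** SAP 13 reports no difference between its planned analyses and the protocol's.

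**The concern.** Objective 12 has three parts: a change tied to stopping drug at Week 6, a comparison of Arm B with Arms A and C, and a split by nicotine status. The MNWS table in SAP 10.2.11 has none of them in usable form. Its reference is the Day 0 score, it pools all nicotine statuses within an arm, and it gives no contrast or interval.

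The split is the part that matters most. A subject who is still smoking at Week 6 still has nicotine when cytisinicline is withdrawn. A subject who is abstinent does not. If withdrawal appears mainly in the second group, the pooled arm mean understates it, and a flat Arm B mean could be reported as evidence that stopping at six weeks is free of withdrawal. That is a statement about the six-week regimen that readers will care about, even from an exploratory analysis.

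**Working it through.** The plan states no figure for this analysis, so there is none to reproduce. The check is a comparison of sections, followed by two calculations.

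**1. Does any section supply the missing parts?**

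| SAP section | Week 6 to 7 within-subject change | B vs C or B vs A with interval | Nicotine-status split |
|---|---|---|---|
| 10.2.11 (MNWS by arm and visit) | No | No | No |
| 10.2.10 (by endpoint success/failure) | No | No; no arm split stated | No |
| 11.1 (adverse events, Week 6 to 7) | Not MNWS | No tests planned (SAP 11) | No |
| 10.2 (general comparisons) | No | Named, but 10.2.11 specifies only description | No |
| 10.2.4 (other nicotine use) | No | For product use only | Never linked to MNWS |

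Endpoint success or failure is not nicotine status at the switch. One primary endpoint covers Weeks 9-12, after Week 7. The endpoints rest on cigarettes and CO, so a subject using other nicotine products can be a success. Failures include subjects with missing data.

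**2. What can be recovered from the by-visit table?**

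With the same subjects at both visits, mean(W7 - baseline) - mean(W6 - baseline) = mean(W7 - W6), so each arm's mean shift follows by subtraction. If the subject sets differ, this is only approximate. In one simulated arm of 250 with complete data, both routes gave 0.207. With about 10% of subjects missing at Week 7, subtraction gave 0.234 and the paired mean was 0.215.

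The precision cannot be recovered. With equal visit SDs, the SD of the change is SD × sqrt(2(1 - ρ)), where ρ is the Week 6 to Week 7 correlation. The documents do not give ρ. Over an assumed range:

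- ρ = 0.3: sqrt(1.4) = 1.18 SD
- ρ = 0.6: sqrt(0.8) = 0.89 SD
- ρ = 0.9: sqrt(0.2) = 0.45 SD

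**3. How much does pooling nicotine statuses dilute the effect?**

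If an effect d occurs only in abstinent Arm B subjects, whose share is p, the pooled arm mean shows p × d. Inputs:

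- n = 250 per arm (SAP 2.2).
- p = 19%: the Week 24 design assumption (SAP 2.2), a low proxy for Week 7.
- p = 30%: ORCA-1, 3 mg TID, Weeks 5-8 (Protocol 4.3).
- p = 50%: ORCA-1, 3 mg TID, Week 4 point abstinence (Protocol 4.3).
- Assumptions: d = 0.5 SD, SD = 1 for the score analysed in the whole arm and in the subset, and equal p in Arms B and C.

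Power for B vs C at two-sided 0.05 is about Φ(effect × sqrt(n/2) - 1.96). At p = 30% pooled: 0.15 × sqrt(125) - 1.96 = -0.28, giving 38.9%. In the abstinent subset of 250 × 0.30 = 75 per arm: 0.5 × sqrt(37.5) - 1.96 = 1.10, giving 86.5%.

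| Abstinent share | Pooled effect | Pooled power | Abstinent per arm | Subset power |
|---|---|---|---|---|
| 19% | 0.095 SD | 18.5% | 48 | 68.8% |
| 30% | 0.15 SD | 38.9% | 75 | 86.5% |
| 50% | 0.25 SD | 79.8% | 125 | 97.7% |

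No test is planned here. Power only measures how visible the effect would be.

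**4. How large is the abstinent placebo group?**

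From the same sources, 7%, 8% and 10% of 250 give about 18, 20 and 25 subjects. In the middle case (75 vs 20), the 95% half-width for B-A is 1.96 × sqrt(1/75 + 1/20) = 0.49 SD. For B-C (75 vs 75) it is 1.96 × sqrt(2/75) = 0.32 SD.

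**The case against.** The strongest reply is that the plan is less empty than it looks. SAP 10.2.11 lists actual values, so Week 6 and Week 7 means appear side by side for three randomised arms. A Week 7 rise in Arm B that is absent in Arm C would be visible. The adverse-event table targets the same switch. The objective is exploratory, and SAP 10.3 allows further analyses. All of this is true. It does not supply the nicotine-status split or an interval, and analyses under SAP 10.3 are to be labelled data-directed, which is a poor home for an objective stated in advance.

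A reader might infer several stronger points that the documents do not support:

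- **That change from baseline is the sole MNWS analysis.** Actual values, percent change and the SAP 10.2.10 description are also planned.
- **That the plan cannot show a withdrawal effect.** It can, descriptively and possibly diluted.
- **That a pre-quit baseline biases the result by mixing six weeks of quitting with the one-week switch.** Arms B and C have the same treatment to Week 6 (Protocol 7.2), so these effects cancel in expectation in B vs C. What remains is a question of precision, and the gain depends on an unknown correlation. Against the actual Week 7 value, the standard-error ratio is sqrt(2(1 - 0.7)) = 0.77 or sqrt(2(1 - 0.6)) = 0.89 for assumed correlations of 0.7 and 0.6. Below 0.5 the change score is the noisier one.
- **That the Week 7 MNWS was scheduled for Objective 12.** This is plausible, since QSU-Brief stops at Week 6, but no section says so.

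**Conclusion.** The gap is real and narrow. No SAP analysis delivers Objective 12: the nicotine-status split is absent, and so are a within-subject Week 6 to Week 7 change and any Arm B contrast on MNWS with an interval. This finding rests on the text alone.

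Its size rests on assumptions. If withdrawal is confined to abstinent subjects, the planned table shows 19% to 50% of it. For an assumed 0.5 SD effect, power for B vs C falls from 69%-98% in abstinent subjects to 18.5%-80% pooled. If withdrawal is equally strong whatever the nicotine status, there is no dilution, and only the missing interval and the unmet objective remain.

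This is a low-cost improvement. Objective 12 is exploratory, and no primary or secondary conclusion depends on it.

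**What to change.** Add a paragraph and one exploratory table to SAP 10.2.11:

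1. **Measure:** Week 7 minus Week 6 change in MNWS total, in subjects with both scores, by arm.
2. **Contrasts:** B-C as the main contrast and B-A as the second, each with a 95% CI.
3. **Strata:** smoking, abstinent, or using other nicotine products, defined from self-report, CO and product use at the Week 6 visit. For B-C, treatment is the same up to that point, so the contrast keeps its randomised basis within strata. For B-A, status is post-randomisation and may already reflect treatment, so label it descriptive.
4. **Timing flag:** the Week 6 visit is Day 42 ± 1, and six 7-day packs end on Day 42. A Day 43 visit can follow the first Carton 2 dose, and MNWS covers the past 24 hours. Flag these visits from the treatment diary, which SAP 11.1 already uses for dosing dates.
5. **Supportive split:** repeat by Week 7 status, which is the closer reading of the objective but can itself be changed by relapse after the switch.

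While editing 10.2.11, point the scoring reference to Section 6.4.2, where the rules are; Section 8.6 only refers back to it.

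Cost: one table and a short paragraph, with no new data collection and no effect on alpha. The downside is small strata, above all abstinent placebo subjects, so B-A there will be imprecise.
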